1.1 Objectives and Hypotheses

The main objective of the SHAPE pilot study is to determine the feasibility of using Habit Formation (HF) treatment to increase Physical Activity (PA) (reduction in daily in hours of sedentary time), and dietary among prefrail African Americans. This study will test two hypotheses:

***Hypothesis 1:** The SHAPE study will demonstrate good feasibility with high recruitment rate and successfully administrating all of measures among the target population.*

***Hypothesis 2:** Treatment group participants will demonstrate greater increases in primary outcomes (sedentary time and dietary quality) and secondary outcomes (prefrailty reduction, lower extremity strength, balance, and quality of life) at intervention completion.*

[figure not shown]

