1.3 Study design

The SHAPE pilot study is a two-armed, single blinded, randomized control trial study (Figure 2). Community dwelling prefrail African Americans ages 55 and older is the target population to account for accelerated aging among African Americans.⁶⁶ The sampling frame are African American adults who register in the Healthier Black Elders Center's Participant Resource Pool (PRP). The screening, consent, and enrollment procedures will follow a strict IRB-approved protocol over 16 weeks. Eighty prefrail African Americans will be randomized to the treatment or control group.

[figure not shown]

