2.1 Data analysis

Feasibility outcomes such as recruitment, retention, and attendance data were presented by descriptive statistics. Differences in baseline characteristics between the two groups were tested by independent t tests or chi-square/Fisher's exact tests. For the primary and secondary outcomes, effect sizes were represented by Cohen's D, where 0.2 indicates small, 0.5 as moderate, and 0.8 as large effects. As for mechanisms of behavior change, pre and post habit formation effect sizes are estimated by Cohen's D. All statistical analyses were conducted by IBM SPSS software, version 26.0 (SPSS Inc., Chicago, IL).

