2.2 Sample size estimation

We did not use power analysis to estimate study sample size for determine efficacy. We aim to recruit 15 participants in per group suggested for feasibility pilot study.

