2.3 Assessments

Primary outcomes (measured at week 0 and 1 week post intervention). Sedentary Time (ST) was measured via the ActivPal wireless activity tracker. ActivPal is a validated tool with a commercialized program to generate mean minutes of total ST (min/day), sum of 30-minute bouts ST, and sum of 60-minunite bouts ST, as well as the number of 30-min bout ST and 60-minutes bout ST per day. Participants wore the ActivPal device on their thigh for seven days during their waking hours. Dietary Quality was measured using the Healthy Eating Index (HEI) and operationalized as the total HEI score generated from the National Cancer Institute's ASA 24®.

Secondary outcomes (measured at week 0 and 1 week post intervention). Pre-frailty status was measured using the current gold standard, the Cardiovascular Health Study frailty criteria as composite index consisting of the following components: (a) self-reported weight maintenance; (b) walking speed (the mean time of two trials for the time taken to walk 15 ft. reported in seconds); (c) grip strength, (mean score of grip strength reported in Lbs. of three trials on the dominant hand using a calibrated Jaymar dynamometer); (d) exhaustion, measured as a response of "All of the time" or "Most of the time" to the following two questions reported on a 4 point Likert scale, "I felt that everything I did was an effort in the last week," and "I could not get going in the last week"; and (e) total Kcals of energy expended over a 7 day period, measured via Community Healthy Activities Model Program for Seniors (CHAMPS) questionnaire. Change of all PA and MVPA duration (minutes/week) measured by CHAMPS. We also used Activpal to estimate the cumulated MVPA duration. We cumulated MVAP minutes by selecting activity intensity greater than 3 METs. Physical Function was measured via the Short Physical Performance Battery (SPPB) subtests for lower extremity strength and balance. Depressive symptoms were measured using the Geriatric Depression Scale (Kieffer & Reese, 2002). Participant anthropometry such as weight circumference (inch) was measured by a girthometer, height (cm) by a stadiometer, and weight (pound) by medical scales. Body mass index (BMI) was also calculated based on participant anthropometry. Quality of life was measured using the 26-item validated WHOQOL-BREF. Occupational performance was

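### Feasibility is the main objective, but Hypothesis 1 has no criterion, two conflicting recruitment targets and no planned summary of measure completion; Cohen's d is labelled without an interval

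*Combined protocol and SAP*

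**What the plan says.** Section 1.1 opens with the aim: "The main objective of the SHAPE pilot study is to determine the feasibility of using Habit Formation (HF) treatment". It then says the study will test two hypotheses. Hypothesis 1 reads: "The SHAPE study will demonstrate good feasibility with high recruitment rate and successfully administrating all of measures among the target population". Hypothesis 2 begins: "Treatment group participants will demonstrate greater increases in primary outcomes (sedentary time and dietary quality".

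Section 2.1 gives feasibility one sentence: "Feasibility outcomes such as recruitment, retention, and attendance data were presented by descriptive statistics". It summarises primary and secondary outcomes by Cohen's d, with 0.2, 0.5 and 0.8 marking small, moderate and large. It mentions no interval.

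On size, section 2.2 says "We did not use power analysis to estimate study sample size for determine efficacy" and aims for 15 participants per group, a number it attributes to feasibility-pilot practice. Section 1.3 says that eighty people will be randomised, and adds: "The screening, consent, and enrollment procedures will follow a strict IRB-approved protocol over 16 weeks".

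The outcomes labelled primary in section 1.1, Table 1 and section 2.3 are sedentary time and dietary quality. Neither Table 1 nor section 2.3 lists a feasibility measure.

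**The concern.** Hypothesis 1 has two parts: recruitment is high, and all measures are successfully administered. For the first, the plan reports a figure but does not say what would count as high, over which denominator, or against which of two targets. For the second, it names no summary.

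The second part is a real question in this population. Section 1.3.4 asks for seven consecutive days of ActivPal wear, a pick-up visit, and two ASA24 recalls on non-consecutive days. Table 1 repeats these measures at follow-up. Incomplete data here are what a pilot should find and report before a larger trial.

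If nothing is fixed, the judgement of good feasibility will be made after the numbers are known. A related risk concerns the outcomes: a size label on d with no interval invites a reader to treat a very imprecise estimate as a finding.

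**Working it through.** **Step 1. Can the plan's own sample size be reproduced?** No. The documents give no alpha, power, standard deviation, precision target or feasibility threshold behind 15 per group or behind 80.

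**Step 2. Hypothesis 1 set beside section 2.1.**

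| Element | In Hypothesis 1? | Summary named in 2.1? | Criterion stated? |
|---|---|---|---|
| Recruitment | Yes | Yes, descriptive | No |
| Administration of all measures | Yes | No | No |
| Retention | No | Yes, descriptive | No |
| Attendance | No | Yes, descriptive | No |

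**Step 3. Is there an implied recruitment benchmark?** The totals are 80 (section 1.3) and 2 × 15 = 30 (section 2.2); 80/30 = 2.7. If the 16 weeks of section 1.3 are the enrolment window, the implied rates are 80/16 = 5.0 per week and 30/16 = 1.9 per week. Accrual of 3 per week would beat one and miss the other. The reading of the 16 weeks is an assumption: Table 1 runs from week 0 to week 15, also 16 weeks, so a per-participant timeline is possible.

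**Step 4. How precise would a feasibility proportion be?** The documents give no expected rate, so 80% is an assumed illustration. The exact (Clopper-Pearson) 95% limits for x out of n are the 2.5% point of Beta(x, n − x + 1) and the 97.5% point of Beta(x + 1, n − x).

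| Observed | Rate | Exact 95% CI |
|---|---|---|
| 12/15 (one arm, for example session attendance) | 80% | 52% to 96% |
| 24/30 | 80% | 61% to 92% |
| 64/80 | 80% | 70% to 88% |

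**Step 5. Does the form of the decision rule matter?** Yes. Under an illustrative cut-off of 80%, 24/30 passes on the point estimate. If the lower limit must exceed 80%, 28/30 fails (lower limit 77.9%) and 29/30 passes (82.8%). With 80 participants, 71/80 fails (79.7%) and 72/80 passes (81.2%). A cut-off without a rule is therefore not enough.

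**Step 6. How precise is Cohen's d?** With n per arm, SE(d) ≈ √(2/n + d²/(4n)) and the 95% half-width is 1.96 × SE. Take d = 0.5, the plan's moderate benchmark.

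- n = 15: SE = √(0.1333 + 0.0042) = 0.371; half-width 0.73; interval −0.23 to 1.23.
- n = 40: SE = √(0.0500 + 0.0016) = 0.227; half-width 0.45; interval 0.05 to 0.95 (unrounded half-width 0.445).

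At 15 per arm, a result labelled moderate is compatible with anything from a small effect in the wrong direction to one well above the plan's large benchmark. At 40 per arm, it spans negligible to large.

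**The case against.** **Pilots are descriptive.** This stands. Nothing here asks for a significance test of feasibility. But the plan itself says Hypothesis 1 will be tested, and a descriptive figure can answer it only if the plan says what answer counts.

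**The list in section 2.1 is open-ended.** Its wording does not exclude a completion summary. It does not specify one either, and this is half of the main hypothesis.

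**Some results would plainly contradict Hypothesis 1.** This also stands. A large recruitment shortfall, or a measure that could not be given at all, would count against it. A reader might infer that almost any result could be called good feasibility; that goes too far. The gap is for results between the extremes.

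**The primary outcomes are not foreign to the objective.** A reader might infer that efficacy measures have displaced feasibility, so that the labels contradict the main aim. The documents do not support this: the objective in section 1.1 concerns using the treatment to change sedentary time and diet, so both outcomes sit inside it. Relabelling is a preference.

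**Low power is not the point.** A reader might calculate power for a between-group test and call the design inadequate. Section 2.1 plans no such test on primary or secondary outcomes; t and chi-square or Fisher tests are for baseline characteristics. Nor does section 2.2 say that effect estimates are unsupported, only that no power analysis was used for efficacy. What matters is the width of the interval around d.

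**Conclusion.** The concern holds in limited form. Three gaps bear on the main objective: no statement of what recruitment counts as high, two targets that differ 2.7-fold (80 against 30), and no named summary of measure completion. A fourth bears on Hypothesis 2: Cohen's d is labelled by size with no interval, when an observed 0.5 carries about ±0.73 at 15 per arm or ±0.45 at 40 per arm, and the hypothesis is worded as something the trial will show.

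The absence of a criterion, the conflict of targets and the missing summary rest on the text alone. The 80% figures are illustrations, not document values. The weekly rates depend on reading the 16 weeks as the enrolment window. The half-widths use a large-sample approximation and assume that all randomised participants contribute data; dropout would widen them.

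This should be changed: the pilot's main conclusion depends on it and the repair is cheap.

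**What to change.** 1. **Recruitment.** Reconcile 80 with 15 per group across sections 1.3 and 2.2. Judge recruitment against that single target, within the 16 weeks if section 1.3 is confirmed to mean the enrolment window. Also report it as randomised/contacted and randomised/eligible.
2. **Completion.** Add to section 2.1 the proportion of randomised participants completing each measure at baseline and at follow-up: seven-day ActivPal wear, both ASA24 recalls, SPPB, Fried components and questionnaires. Report it with retention and attendance, each with an exact 95% CI.
3. **Criterion.** State one sponsor-chosen cut-off per feasibility measure, and whether the point estimate or the lower confidence limit decides. Fix it before enrolment or before the data are seen. Sections 1.3.5, 2.1 and 2.3 are partly in the past tense, so this may no longer be possible; if so, label any cut-off post hoc.
4. **Effect sizes.** Report Cohen's d with a 95% CI, and reword Hypothesis 2 from demonstrating greater gains to estimating the difference between groups.

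Relabelling sedentary time and the HEI score as preliminary efficacy outcomes is optional.

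The cost is protocol and SAP wording, a contact and eligibility log for the denominators, and some proportions and intervals, mostly from data the study collects anyway. Settling the sample size is a decision for the sponsor rather than an edit. The downside is that the sponsor commits to cut-offs it could miss.

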1.2 Background

Frailty among older African Americans is common, detrimental and costly. Approximately 50% of older adults are pre-frail,¹⁻² which makes them 2-3 times more likely to develop frailty within 3-7 years than non-frail elders.²⁻⁵ Frailty, is defined as a decline in resilience across one or more domains of functioning that reduces an individual's ability to respond to or recover from stressors (e.g., illness or loss of a loved one).⁶ In the context of frailty, acute social or health stressors can trigger a cascade of negative sequelae. Frail older adults are more likely to experience premature morbidity (as high as a 50% increase in relative risk),⁴ mortality, and institutionalization.^{1-2, 4, 7-8} African Americans have an especially high risk of becoming frail. African Americans are 2-4 times more likely to develop frailty than their European American counterparts, to do so at a younger ages, and to experience worse outcomes as a result.^{1, 9-10} Moreover, correlates of frailty such as having less formal education and lower income,¹² living in lower quality neighborhoods,¹²⁻¹⁵ higher rates of comorbid chronic diseases, obesity, and of disability are more prevalent in African American populations.¹⁶⁻²¹

Effective frailty reduction interventions delivered to older African Americans during the prefrailty stage could reduce or delay frailty and improve health outcomes among older African Americans. For prefrail older adults, the progression to frailty is neither inevitable nor irreversible. Pre-frail elders can regain non-frail resilience and are significantly more likely to do so than frail elderly.^{5, 22-24} Moreover, pre-frailty represents an important, time-limited window of opportunity to intervene in the progression to frailty.²⁵ A recent study suggested that individual's spend approximately 7.4 years in the prefrail stage versus only 3.4 in the frail stage (before progressing to death or disability).²⁵ Interventions delivered during prefrailty may also require less intensive treatment than those delivered during frailty. Resilience-bolstering behaviors such as consuming adequate nutrition and increasing physical activity (PA) levels are currently the frontline non-pharmacological treatment for frailty reduction. Adequate nutrient intake (e.g., protein, vitamin D, fatty acids and minerals) protects against frailty by improving cell metabolism and anabolic signaling.²⁶ PA is considered frailty-protective through the effect that it has on attenuating sarcopenia,²⁶⁻²⁷ stimulating muscle protein synthesis,²⁸⁻²⁹ and

increasing muscle strength, and physical performance.²⁶⁻²⁷ Thus, intervening to increase physical activity and improve dietary quality among older adults during the prefrailty stage has the potential to reduce prefrailty and significantly improve both current and future health.

A novel, evidence-based habit formation program is used the SHAPE study to improve dietary quality and decrease total sedentary time (ST) could reverse prefrailty or delay its progression among older adults. The habit formation program consists of 12 treatment sessions over 12 weeks. In each session, an occupational therapist will deliver educational content, and use HF techniques and behavioral skills to facilitate frailty protective behaviors. The conceptual treatment model approach to improve dietary quality and reduced ST among frail older adults (Error! Not a valid bookmark self-reference.). HF approaches are effective across a range of behaviors, easy to implement, satisfactory to participants, tailorable to the individuals' unique context, and correlated with key health outcomes.^{54, 63-65}

1.3 Study design

The SHAPE pilot study is a two-armed, single blinded, randomized control trial study (Figure 2). Community dwelling prefrail African Americans ages 55 and older is the target population to account for accelerated aging among African Americans.⁶⁶ The sampling frame are African American adults who register in the Healthier Black Elders Center's Participant Resource Pool (PRP). The screening, consent, and enrollment procedures will follow a strict IRB-approved protocol over 16 weeks. Eighty prefrail African Americans will be randomized to the treatment or control group.

[figure not shown]

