1.3.5 Randomization and Blinding

After consent/baseline evaluation visit. The study coordinator will check participants' eligibility. Randomization was carried out by a coordinator not involved in data collection or analysis activities. Data collectors were blinded to arm assignment.

Participants will be allocated using a 1:1 ratio via adapted randomization sequences generated *a priori* by the study statistician, [name], using an online tool (<https://www.sealedenvelope.com/simple-randomiser/v1/lists>) to form a randomization table with a variable block size (2,4, or 8). Randomization sequence concealment will be achieved by query of the REDCap (Research Electronic Data Capture) system.

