1.3.7 Intervention period

The treatment group will receive habit formation intervention for 12 weeks. The HF intervention is delivered by an experienced geriatric occupational therapist. The 12-week long, intervention is delivered to each participant during 12 face-to-face, home based sessions (each lasting ~60 minutes). An initial session (week 2) focuses on welcoming the participant to the program, and delivering educational content about prefrailty, frailty protective behaviors, and the concept of HF. In preparation for the sessions covering ST reduction and MVPA the next session (week 3) focuses on pain, its management, and the relationship between pain and activity (described below). Weeks 3-11 include weekly HF sessions focused on ST reduction, MVPA and dietary behaviors (see Table 2 for session content). A closing session occurs in week 12 to review program progress and create maintenance plans.

The control group will receive 12 weeks of newsletters focused on general healthy aging topics. Within 4 days of mailing the newsletter, the coordinator will call the participant, verify receipt of the newsletter, and ask them if they have any questions about the materials. Phone

call will last ~15 minutes. Control condition participants receive no further intervention.

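### Section 1.3 says 80 participants will be randomised (40 per arm), section 2.2 aims for 15 per group (30 in total), and no text reconciles the two

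*Combined protocol and SAP*

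**What the plan says.** Section 1.3 (Study design) describes a two-arm randomised pilot and gives its size: "Eighty prefrail African Americans will be randomized to the treatment or control group". Section 1.3.5 (Randomization and Blinding) sets the split: "Participants will be allocated using a 1:1 ratio".

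Section 2.2 (Sample size estimation) says that no power analysis was used to size the study for efficacy. It then gives a different target: "We aim to recruit 15 participants in per group suggested for feasibility pilot study".

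Three other places bear on the consequences:

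- Section 1.3.7, on the treatment arm: "intervention is delivered to each participant during 12 face-to-face, home based sessions", each lasting about an hour.
- Section 1.1, where Hypothesis 1 expects "good feasibility with high recruitment rate and successfully administrating all of measures". It gives neither a denominator nor a threshold for the recruitment rate.
- Section 2.1: "Feasibility outcomes such as recruitment, retention, and attendance data were presented by descriptive statistics". The same section reports the primary and secondary outcomes as Cohen's d, with 0.2, 0.5 and 0.8 as the small, moderate and large benchmarks.

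**The concern.** The number randomised is a basic design parameter, and the plan gives two values for it. Three things depend on which is right.

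- **Delivery.** The number in the treatment arm fixes how many home sessions the occupational therapist must provide.
- **Precision.** The outcomes are to be summarised as effect sizes, and the width of any interval around them depends directly on the number per arm. A reader cannot tell which precision was planned.
- **Feasibility.** Feasibility is the main objective. If recruitment is judged against the planned number, the same enrolment could be called complete or well short, and the target could be picked once the result is known. If the rate is enrolled over approached, the percentage does not depend on the target. The documents do not say which is meant.

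**Working it through.** **Inputs.** Total randomised 80 (1.3). Target 15 per group (2.2). Two arms (1.3). Ratio 1:1 (1.3.5). Twelve home sessions per treated participant (1.3.7). Cohen's d benchmarks 0.5 and 0.8 (2.1). There is no power calculation to reproduce, because 2.2 says none was used.

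**Step 1: the two sizes.**

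- From 1.3: 80 / 2 = 40 per arm.
- From 2.2: 2 × 15 = 30 in total.
- Difference: 80 − 30 = 50. Ratio: 80 / 30 = 2.67.

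**Step 2: can the figures be reconciled?**

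- *Dropout.* No rate is stated. Inflating 30 by N / (1 − d) gives 30 / 0.8 = 37.5, so 38, at 20% dropout, and 30 / 0.5 = 60 at 50%. Reaching 80 needs d = 1 − 30/80 = 62.5%. Section 2.2 also speaks of recruiting, not of completing.
- *Screened versus randomised.* Section 1.3 attaches the 80 to randomisation. Section 2.2 counts by group, and groups exist only after randomisation.
- *Staged design or a later trial.* None is described. Section 1.3 attaches the 80 to the SHAPE pilot study, and 2.2 attaches the 15 per group to a feasibility pilot.

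**Step 3: delivery.** 12 × 15 = 180 sessions against 12 × 40 = 480, a difference of 300.

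**Step 4: recruitment against plan (conditional on that reading).** If 30 are randomised, 30/30 = 100% of the 2.2 target and 30/80 = 37.5% of the 1.3 target.

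**Step 5: precision of Cohen's d.** Section 2.1 does not say whether the outcome effect sizes are between-group. I assume they are, because Hypothesis 2 compares the groups, and I assume no dropout. The approximate 95% half-width with n per arm is 1.96 × √(2/n + d²/(4n)).

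| d | n = 15 | n = 40 |
|---|---|---|
| 0 | 1.96 × √0.1333 = 0.72 | 1.96 × √0.0500 = 0.44 |
| 0.5 | 1.96 × √0.1375 = 0.73 | 1.96 × √0.0516 = 0.45 |
| 0.8 | 1.96 × √0.1440 = 0.74 | 1.96 × √0.0540 = 0.46 |

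For an observed d of 0.5, the interval is −0.23 to 1.23 at 15 per arm and 0.05 to 0.95 at 40 per arm. An exact noncentral-t calculation gives almost the same: −0.232 to 1.223 and 0.053 to 0.944. The first interval includes zero; the second does not.

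*Sensitivity.* With 20% dropout (my assumption, not in the documents), 12 and 32 per arm remain. The half-widths near zero are then 1.96 × √(2/12) = 0.80 and 1.96 × √(2/32) = 0.49.

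**The case against.** The contradiction itself is hard to dispute, so the case on the other side concerns its weight and framing.

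- **Figure 2 is not in the text available for review.** A study overview might carry participant numbers. It could show which figure was intended, but it could not make both sentences true. This limits the claim to saying that no available text reconciles them.
- **Nothing formal depends on N.** This is a feasibility pilot with no efficacy power claim, descriptive feasibility summaries and no decision threshold. That is true, and it means no planned test is invalidated. It does not make a 2.7-fold conflict in the number randomised acceptable.
- **The precision figures are illustrations.** The plan states no precision target and does not say that its Cohen's d is between-group. This stands: keeping 30 would change only the stated size, and the precision figures are mine. The contradiction does not rest on them.
- **The recruitment argument is conditional.** The undefined recruitment rate is a separate gap, and 37.5% matters only if recruitment is judged against plan. This also stands, and the finding would hold without it.
- **The documents do not show which figure is right.** Agreed. The correction should follow whichever figure was operative.

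**Conclusion.** The concern holds. Sections 1.3 and 2.2 give 80 and 30 for the same quantity in the same pilot, and both cannot be correct. The conflict needs only the two-arm design and the 1:1 ratio, both stated in the protocol. The gap of 50 participants and the 180 versus 480 sessions follow directly from stated figures. The half-widths of about 0.72 and 0.44 near d = 0 rest on a between-group d and no dropout. The 100% versus 37.5% contrast rests on judging recruitment against plan. The documents do not establish which size was intended. Because the number randomised is fundamental to the design and the correction is simple, this must be fixed.

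**What to change.** State one number in both sections and say that it counts participants randomised:

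- If 15 per group is the operative target, change 1.3 to 30 (15 per arm). The stated size becomes less favourable, and so does the precision it implies.
- Change 2.2 to 40 per group only if 80 was the operative and resourced figure.

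Report recruitment against that single figure. Much of section 2 is in the past tense, so if the study has already run, disclose which figure was operative and when it was set, so that the target is not seen to be chosen to fit the enrolment achieved.

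**Cost.** A wording amendment to 1.3 or 2.2, with no extra participants if 30 is kept or if 80 was already resourced. If the study was resourced for 30 and 80 is chosen, the cost is 80 − 30 = 50 more participants and 480 − 180 = 300 more home sessions.
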